1.0 INTRODUCTION

1.1 Disease Specific Background

The malignant gliomas are rarely controlled by any treatment and are almost uniformly fatal. Survival following conventional neurosurgical intervention and radiotherapy can be measured in terms of months and reported survival frequencies are in the range of 55-67% at 6 months, 27-39% at 12 months, and 8-20% at 24 months. Relentless local growth of tumor rather than metastases kills the patient.

Considerable effort has been made by investigators in recent years to search for newer avenues of approach, including higher doses of conventional photon radiation, combination of chemotherapy and photon radiation, and high LET radiations.

The RTOG and ECOG have a joint current protocol (RTOG 74-01) which tests standard whole brain radiation using photons to a total dose of 6,000 rad against the same radiation dose with a 1,000 rad boost added, or the addition of chemotherapy using BCNU or methyl CCNU + DTIC. Over 600 patients have been randomized. The study was closed in March, 1979, and preliminary analysis shows no difference among the four treatment randomizations. These preliminary findings are consistent with the early reports of the Brain Tumor Study Group investigation of radiation alone versus radiation plus BCNU.

Inasmuch as there are theoretical biological bases for better responses of the tumors to high LET radiation, pilot studies with fast neutron whole brain radiotherapy were undertaken and some initial observations are available.

Thirty-three patients treated at the University of Washington in Seattle and 35 patients treated at Hammersmith, England, showed excellent tumor control with autopsy data showing better than 90% of the patients with gross tumor replaced by

0015921

coagulation necrosis and only reactive astrocytes in the region. However, diffuse gliosis and demyelination suggested that the RBE for neutrons in the brain may be nearly 4 rather than 3. Dosage was reduced 20% which resulted in no observable brain damage, but patients died of persistent, viable tumor.

A current RTOG protocol (RTOG 76-11) is evaluating the combination of photon radiation to 5000 rad with a neutron boost of 500 rad (approximately equivalent to 1500 photon rad). Although this study is still accruing patients and has yet to mature, a dramatic gain has not been demonstrated in the preliminary results of the first sixty patients.

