This study established the maximum tolerated dose for one dose/week for 3 weeks as $4 \text{ gm/m}^2/\text{dose}$ or a total of 12 gm/m^2 in three weeks. At this dose approximately 50% of the patients will have measurable peripheral neuropathy, but this neuropathy will rarely exceed Grade II, i.e., sensory only of a moderate degree.

This study also established that for weekly administration for 6 weeks, 15 gm/m^2 was the maximum tolerated dose. At this dose level over this time period also, approximately 50% of patients experienced peripheral neuropathy of a Grade I-II nature with only occasional patients experiencing more severe neuropathies. More severe neuropathies were always associated with advanced age, marked dehydration, excessively high blood levels, or a pre-existing severe neuropathy such as from vincristine.

0015923

Subsequent to this publication by Wasserman, et al, an additional 64 patients have been treated on multiple doses/week schedules. With administration twice per week a dose of 1.5 gm/m^2 was given to 6 patients for 6 weeks or 12 doses. Two patients died during the study and one withdrew. Of the three patients completing treatment, one had a Grade II, one a Grade III, and one a Grade IV neuropathy with encephalopathy. It was assumed that this was too high a dose. Fourteen patients were then given 12 doses of 1.25 gm/m^2 over 6 weeks. Of these only one died during treatment and one withdrew. No drug related deaths were noted. Three patients experienced Grade I neuropathies and four Grade II neuropathies with no neuropathies of a more severe nature. It was thus determined that the maximum tolerated dose in 6 weeks, with 12 doses was 1.25 gm/m^2 or a total of 15 gm/m^2 . Thus, the total dose could not be increased by dividing it into two rather than one administration per week.

Thus, it would appear that fractionation of the drug dosage has no effect on drug tolerance as related to neuropathy. Smaller incremental doses do, of course, markedly reduce nausea and vomiting. The maximum tolerated dose, regardless of fractionation, appears to be approximately 8 gm/m^2 in one week, 10.5 gm/m^2 in 1.5 weeks, 12 gm/m^2 in 2-3 weeks and 15 gm/m^2 in 6 weeks.

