4.0 PRETREATMENT EVALUATION

4.1 General Evaluation.

- 4.1.1 A complete history and physical, including the documentation of all measurable disease is necessary. Special attention should be directed to a careful neurologic examination, including cranial nerves, mental status, visual status, peripheral reflexes, peripheral sensation, motor activity and cerebellar function.

4.2 Mandatory Imaging Procedures.

- 4.2.1 CT brain scan done post surgery but prior to the start of radiation.
- 4.2.2 Necessary imaging and/or contrast studies to optimally define the location and extent of the tumor including brain scan, CT scan, echogram, cerebral arteriography and/or air studies, i.e., ventriculogram, pneumoencephalogram.

4.3 Mandatory Laboratory Procedures.

- 4.3.1 CBC including platelets.
- 4.3.2 Serum alkaline phosphatase, SGOT, LDH, total protein, albumin, BUN, creatinine, bilirubin, calcium, sodium, potassium, phosphorus, total protein, uric acid, or other tests to assure acceptable liver and renal function.
- 4.3.3 Complete urinalysis.

- 4.4 Neurologic examination will include functional classification of status as per RTOG (see Appendix V).

0015928

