8.0 PATIENT ASSESSMENTS

8.1 Patient assessment will include the following:

8.1.1 Study Parameters.

	Pre-Treatment	During Treatment	Each Follow-up
History and Physical (including neurological assessments)	x	x	x
Karnofsky Status	x	a	x
Neurological Functional Classification	x	x	x
CT Scan	x		b
CBC, platelets	x	a	b
Urinalysis	x		
BUN, creatinine, uric acid	x	a	b
Alkaline Phosphatase, LDH, SGOT, bilirubin	x	a	b
Electrolytes	x	a	
Total Protein, Albumin	a	a	
Misonidazole Serum level		a	

- a) If receiving misonidazole (see Appendix V for additional assessments).
- b) If indicated.

0015936

- 8.1.2 Misonidazole Toxicity: The frequency, duration and grade of nausea and vomiting occurring in the patient will be recorded and evaluated.
- 8.1.3 The incidence and degree of peripheral and central neurologic toxicity and ototoxicity will be recorded and evaluated as a function of the number of drug administration, total drug dose, and plasma levels.
- 8.1.4 Mean plasma (4-6 hour) blood levels will be recorded for each drug administration and correlated with the observed frequency and severity of gastrointestinal and neurologic toxicity as well as the drug dose administered in terms of mg/m^2 and mg/kg .
- 8.1.5 Reactions to radiotherapy, both acute and late, will be recorded and included in the complete toxicity evaluation (Appendix IV). Toxicity occurring in any organ will be recorded, as will the location of the organ (within or outside of the radiation treatment volume).
- 8.1.6 Late normal tissue reactions should be recorded at the time of each follow-up according to the scale in Appendix VII.

8.2 Criteria for Tumor Response.

- 8.2.1 All neurological exams and CT scans are graded by comparing the results of the current test with the most recent preceding test. The scale below is to be followed:
- | | | | |
|----|-------------------------------------|----|-----------------------|
| -3 | Marked Deterioration | +3 | Marked Improvement |
| -2 | Definite Deterioration | +2 | Definite Improvement |
| -1 | Suspected Deterioration | +1 | Suspected Improvement |
| 0 | No change since previous evaluation | | |

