- 8.2.2 Response is defined as definite (+2) improvement in at least one of these two parameters: neurological examination and CT scan, provided that the patient is on a stable or decreasing dose of steroids. A concomitant increase in steroid dose will rule out a "response" designation at this point. Suspected (+1) improvement will not designate response.

8.2.3 Conversely, progression is defined as definite (-2) deterioration in at least one of these two parameters: neurological exam and CT scan, provided that the patient has not had his/her dose of steroids decreased since the last course of therapy. A concomitant decrease in steroid dose will rule out a "progression" evaluation at that point. Suspected (-1) deterioration will not designate progression.

8.2.4 Stabilized disease (no change) is defined as stability or suspected (+1 or -1) changes in the test parameters, or improvement in one of the parameters, and deterioration in one parameter.

8.2.5 Follow-up assessments are to be done midway through treatment, upon completion of radiotherapy, then every three months until death. Patients receiving misonidazole are to have assessments done prior to each treatment according to misonidazole study parameters (Appendix VI). Every attempt should be made to obtain an autopsy for confirmation of tumor types and for studying radiation-sensitizer effects on normal brain.

8.3 Measurement of Specific End Points.

8.3.1 Relapse free interval will be measured from the first day of treatment until deterioration is documented as defined in 8.2.

8.3.2 Overall survival will be measured from the first day of radiotherapy until death.

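### Section 8.2.3 lets a definite neurological deterioration count alone as tumour progression with no toxicity exclusion, so some misonidazole neurotoxicity can be scored as progression

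*Protocol*

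**What the plan says.** **The rule.** Protocol 8.2.3: "progression is defined as definite (-2) deterioration in at least one of these two parameters: neurological exam and CT scan". Two things can prevent the call. One is the steroid clause, which begins "A concomitant decrease in steroid dose will rule out a" and covers a progression call at that evaluation. The other is 8.2.4, which classes improvement in one parameter with deterioration in the other as stabilized disease. Toxicity is not mentioned in either place.

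**What is graded.** Protocol 8.2.1: "All neurological exams and CT scans are graded by comparing the results of the current test with the most recent preceding test". It has no step that separates tumour from treatment as the cause of a change.

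**What the examination contains.** Section 4.1.1 asks for a "careful neurologic examination, including cranial nerves, mental status, visual status, peripheral reflexes, peripheral sensation, motor activity and cerebellar function". Section 6.2.3.2.1 grades peripheral misonidazole toxicity on reflexes, weakness and paresthesia, among other items. Section 6.2.3.2.2 grades central toxicity on mental status, motor and cerebellar function and seizures.

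**How often toxicity is expected.** For 15 g/m2 given weekly over six weeks, section 1.2 reports that "approximately 50% of patients experienced peripheral neuropathy of a Grade I-II nature".

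**Where the rule is used.** Section 8.3.1 ends the relapse-free interval at deterioration as defined in 8.2. Section 10.2 bases further testing on the one-year local control rate (45% against 25%) and does not say how local control is judged.

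**The concern.** Objective 2.2 is tolerance and objective 2.3 is tumour control. As 8.2.3 is written, one neurological event can count against both: a patient who loses reflexes and becomes weak from the drug could be graded as definitely worse and so as progressed. The steroid clause shows that the authors foresaw a cause of neurological change other than tumour growth, but they dealt with only that one. With 25 patients and no control arm, nothing in the design would reveal or offset the error. Misclassification of this kind shortens the relapse-free interval. If the same criteria decide local control, it also lowers the rate on which further testing depends.

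**Working it through.** **1. Is there a safeguard elsewhere in the protocol?**

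- *CT.* The table in 8.1.1 has no CT during treatment, and CT at follow-up only when indicated. Imaging need not be available to bring 8.2.4 into play.
- *Consultant review.* Sections 9.4 and 9.5 cover Grade III and IV reactions only, and give the review no effect on the 8.2 call. The expected neuropathy is Grade I-II.
- *Attribution.* Section 6.2.5 asks whether central effects are thought due to the drug, and 6.2.4 separates neuropathic from other pain. Neither is linked to 8.2.3.

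None of these closes the gap.

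**2. The protocol's own figures (10.2).**

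- Chance of seeing a 1-in-10 complication: 1 − 0.9^25 = 92.8%, which agrees with the stated 93%.
- Local control: no cut-off is stated. A rule of at least 8 of 25, by the normal approximation without continuity correction, gives 20.9% acceptance at 25% control and 90.4% at 45%. Both stated limits are reproduced.
- Exact binomial: at least 8 of 25 gives 27.3% and 93.6%; at least 9 of 25 gives 14.9% and 86.6%. No whole-number cut-off meets both limits exactly, so 8 of 25 is only illustrative.

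**3. Share misclassified.** Let m be the share of truly controlled patients scored as progressed because of toxicity. The documents give no value. The nearest guide is the twice-weekly series in 1.2, with the same 15 g/m2 total over six weeks, in 14 patients: "Three patients experienced Grade I neuropathies and four Grade II neuropathies with no neuropathies of a more severe nature".

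- Any grade: 7/14 = 50%.
- Grade II: 4/14 = 29%, or 4/12 = 33% without the one death and one withdrawal.

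**4. Effect, if local control is judged by 8.2.** The observed rate is 0.45 × (1 − m), and acceptance is the exact P(X ≥ 8) with n = 25.

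| m | Observed control | Acceptance |
|---|---|---|
| 0 | 45.0% | 93.6% |
| 5% | 42.8% | 90.3% |
| 10% | 40.5% | 85.8% |
| 4/14 (every Grade II scored −2) | 32.1% | 58.1% |

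If half of the Grade II cases are scored −2 (m = 2/14), the observed rate is 0.45 × 12/14 = 38.6% and acceptance is 80.9%. Under the normal approximation, acceptance falls from 90.4% to 86.1% at m = 5% and 80.7% at m = 10%. About 25 × 0.45 = 11 controlled patients are expected, so m = 10% is about one patient.

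**The case against.** The case on the other side is substantial, and much of it stands.

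- *A reader might infer that half the patients will be falsely called progressed.* The documents do not support this. The 50% is the incidence of Grade I-II neuropathy. Grade 1 is mild, 8.2.3 requires a definite change, and no text maps toxicity grade onto the −3 to +3 scale. Because each examination is compared with the one before, a neuropathy that develops slowly may never reach −2 in a single step.
- *A reader might infer that one-year local control is biased as a matter of fact.* Only the relapse-free interval is tied to 8.2. Appendix VI records local disease status, total disease status and neurotoxicity as separate items, and the Appendix IV sheet carries a separate disease-status code. The link to 10.2 is an inference.
- *A reader might add neutron brain damage as a second source of known weight.* Section 1.1 does report that "diffuse gliosis and demyelination suggested that the RBE for neutrons in the brain may be nearly 4 rather than 3", but gives no rate of clinical decline. It adds that no brain damage was observable after a 20% dose reduction. It is a possible source without a size.
- *Investigators may attribute signs sensibly in practice.* They may, but 8.2 neither asks for attribution nor records it for the progression call.
- *The content of the examination is listed only for the pretreatment visit.* True. Section 8.1.1 requires neurological assessment during treatment and at follow-up without restating the content, so taking the content to be the same is a reading, though the natural one.

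The objections limit the size and reach of the point. They do not supply the missing exclusion.

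**Conclusion.** The gap is real. As written, 8.2.3 allows some misonidazole neurotoxicity to end the relapse-free interval as tumour progression. The effect on one-year local control is conditional on 8.2 being the criterion for it. The size cannot be fixed from the documents. The acceptance figures assume a cut-off of 8 of 25, a chosen m, and toxicity independent of tumour status. That cut-off itself gives 27.3% acceptance at 25% control, above the protocol's limit of under 25%. The 58.1% figure needs every Grade II case to be scored −2, and its rate comes from 14 patients on a different schedule, so it should not be read as a forecast. A small m is enough to matter: under the exact rule, acceptance drops below the stated 90% once m is slightly above 5%. Overall survival (8.3.2) is unaffected. This should be fixed, but it does not rank as a must-fix. It is not a matter for a later analysis plan, because the protocol sets the definition, examiners apply it at the visit, and attribution not recorded then cannot be reliably recovered.

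**What to change.** Amend 8.2.3 so that neurological deterioration the examiner attributes to misonidazole toxicity does not by itself designate progression. This applies in particular to isolated peripheral signs (reflexes, sensation, peripheral weakness) graded under 6.2.3.2.1 at that visit. Add an attribution field to the follow-up form.

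Central signs (mental status, motor, cerebellar, seizures) should still count as progression unless attributed to the drug. A blanket exclusion of everything graded under 6.2.3.2 would be wrong, because its central items are also signs of glioma growth and true progressions would be lost.

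Code uncertain cases as undetermined. Settle them on later scheduled examinations, on any CT done as indicated, or on the autopsy that 8.2.5 already seeks, and back-date progression if it is confirmed. Report the relapse-free interval and one-year control with undetermined cases counted both ways. State in 10.2 whether local control is judged by 8.2.

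The cost is a change of wording and one form field, with no added visits or mandatory scans. The downside is that a few progressions will be dated later or left undetermined.

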6.0 TREATMENT

6.1 Radiation Therapy.

6.1.1 Patients will be treated in the currently active neutron research facilities using the treatment distances and energies currently available at each of the installations.

6.1.2 Specific simulation is required to insure that the entire cranial contents are included in the treatment volume. The treatment portals should cover the cranial contents with a 1 cm margin. A film of each lateral portal must be obtained and provided to RTOG Headquarters. Appropriate head

holding or other immobilization devices should be used in order to insure reproducibility. The last two treatments are to a reduced volume including the gross disease with a 1 cm margin.

6.1.3 Doses will be specified along the central axis in the midplane of the skull.

6.1.4 Isodose curves, correction for inhomogeneities and off axis corrections are not required. The portals shall be opposing lateral portals covering the cranial contents but avoiding the orbit. Each portal must be treated at each treatment session, except for the boost.

6.1.5 Dose definition and schedule.

6.1.5.1 Treatment will be 1 fraction per week, 300 neutron rad at the midplane of the skull delivered with equal components from each lateral field (for the first four fractions). The final boost may be delivered from one or both sides depending on tumor location.

6.1.5.2 The total number of fractions shall be 4 to the whole brain plus two boosts.

6.1.5.3 The treatment shall be delivered in no more than six weeks. The total dose shall be 1200 neutron rad whole brain plus 600 rad boost.

6.1.6 No time dose modifications are permitted. Occasional delays because of equipment malfunction or transportation difficulties will permit the extension of the overall time to six weeks from five if one fraction is logistically not feasible.

6.1.7 Documentation requirements. After study entry, the radiotherapy prescription and a copy of the radiotherapy portal film, central axis calculations and treatment prescription must be forwarded to RTOG Headquarters within one week. At the completion of therapy, the radiotherapy flow sheet and a copy of the boost film must also be submitted.

0015930

6.1.8 Institutional requirements. Only neutron facilities affiliated with the RTOG are eligible. A laboratory calibrated to measure misonidazole levels must be available to participants.

6.2 Chemotherapy Program.

6.2.1 Misonidazole.

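### Protocol 8.2.3 sets two inconsistent steroid windows for progression, and on either reading progressions are missed or dated late

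*Protocol*

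**What the plan says.** Protocol 8.2.3 defines progression as a definite (-2) deterioration on the neurological examination or the CT scan, "provided that the patient has not had his/her dose of steroids decreased since the last course of therapy". The sentence after it reads: "A concomitant decrease in steroid dose will rule out a 'progression' evaluation at that point".

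Four other provisions decide how this works in practice:

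- 6.1.5.3 fixes one course: "The treatment shall be delivered in no more than six weeks". Under 8.2.5, assessments follow midway, at completion of radiotherapy, and then three-monthly until death.
- 8.2.1 says that each examination and scan is "graded by comparing the results of the current test with the most recent preceding test".
- 8.2.2, the matching rule for response, looks only at current dosing: "A concomitant increase in steroid dose will rule out a 'response' designation at this point".
- 8.3.1 builds the endpoint on these rules: "Relapse free interval will be measured from the first day of treatment until deterioration is documented as defined in 8.2".

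The decision in 10.2 is about local control at one year. That section does not refer to 8.2.

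**The concern.** The two sentences of 8.2.3 look back over different periods. One asks about any decrease since the last course, the other about a decrease that coincides with the assessment. In a regimen of repeated courses the first window would restart each time. Here there is one course, so after treatment ends the window only grows.

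Two centres could therefore score the same patient differently, depending on which sentence they apply. Neither sentence is safe alone, because 8.2.1 moves the comparison forward to the latest test even when the deterioration on that test has been discounted. At stake is the relapse-free interval and, depending on how one-year local control is scored, the decision to go on to a phase III trial (2.1, 10.2).

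**Working it through.** **1. One patient followed through the rules.** Suppose steroids are reduced between completion of radiotherapy and the first three-monthly visit, where the CT shows definite (-2) deterioration. The dose is stable afterwards.

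| Visit | Window: since last course | Window: concurrent decrease |
|---|---|---|
| First three-monthly visit, CT -2 | Not progression | Not progression at this visit |
| Next visit, lesion unchanged from previous scan | Not progression | Grade 0 against previous scan: not progression |
| Next visit, suspected further growth | Not progression | Grade -1: not progression |
| Next visit, definite further growth | Not progression, and the same at every later visit | Progression, dated one visit (about three months) late |

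Reading *course* as the weekly treatment changes nothing, since the last one still falls at the end of the treatment period. In every row where the result is wrong, it is wrong in the same direction: fewer or later progressions and a longer relapse-free interval.

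**2. Status of a blocked call.** 8.2.4 begins: "Stabilized disease (no change) is defined as stability or suspected (+1 or -1) changes in the test parameters". It also covers improvement in one parameter with deterioration in the other. A definite deterioration in one parameter with no improvement in the other fits neither. A blocked call therefore has no category; the text does not make it stable disease or controlled disease.

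**3. The figures in 10.2.** Inputs: n = 25, one-year control of 45% (acceptance over 90%) and 25% (acceptance under 25%).

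- Complication detection: 1 - 0.9^25 = 92.8%, which reproduces the stated 93%.
- Normal approximation: a cut-off giving 90% acceptance at 45% is 0.45 - 1.2816 × √(0.45 × 0.55/25) = 0.322. Acceptance at 25% is then 20.1%, so both bounds can be met.
- Exact binomial: at least 8/25 gives 93.6% and 27.3%; at least 9/25 gives 86.6% and 14.9%. Neither meets both bounds exactly. That is a separate, minor matter, but it is why both cut-offs are shown below. The protocol states neither, so both are assumptions.

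**4. Illustration of size.** Let m be the share of true failures left unscored because of a steroid decrease. The protocol gives no value for m. Assume also that an unscored failure counts as controlled. With true control of 25%:

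apparent control = 0.25 + 0.75 × m

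| m | Apparent control | Acceptance, at least 8/25 | Acceptance, at least 9/25 |
|---|---|---|---|
| 0 | 25% | 27.3% | 14.9% |
| 5% | 0.25 + 0.0375 = 28.75% | 43.3% | 27.4% |
| 10% | 0.25 + 0.075 = 32.5% | 59.6% | 42.7% |

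The expected number of failures is 0.75 × 25 = 18.75, so these values of m mean about one to two patients (0.94 and 1.88).

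**5. Ceiling from survival.** Section 1.1 reports 12-month survival of 27–39%. If deaths count as failures and survival stays in that range, apparent control cannot exceed it. The largest possible m is then (0.27 - 0.25)/0.75 = 2.7% at the low end and (0.39 - 0.25)/0.75 = 18.7% at the high end. Even with every one-year survivor scored as controlled, acceptance is at most 35.6% to 82.1% (8/25) or 21.1% to 69.1% (9/25). At the low end of survival the 5% and 10% rows are thus out of reach; at the high end both are possible.

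**The case against.** The strongest reply is that the second sentence explains the first. It limits the bar to a concurrent decrease at the visit in question, and the response rule in 8.2.2 works the same way. A patient tapered months ago and now on a stable dose could then be scored as progressing. A reader of the first sentence alone might infer that such a patient can never be scored as progressing; the documents do not support that as the only reading. The contradiction remains, because the look-back is part of the definition and nothing says that only a concurrent decrease counts.

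A reader might also infer that a blocked patient stays locally controlled at one year. No section says so: 10.2 does not define local control or tie it to 8.2, and 8.2.4 leaves the blocked call unclassified. Any effect on the 10.2 decision is therefore conditional.

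A further reply is that these tumours grow relentlessly (1.1), so under the narrower window most blocked progressions would be picked up at a later visit. That is fair. The usual effect there is delay, and outright loss needs a worsening that then holds steady. Finally, discounting deterioration that may only reflect steroid withdrawal is a sensible aim. The fault lies in how long the discount lasts and what happens afterwards.

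**Conclusion.** The inconsistency is real and rests on the text alone. On one reading a post-treatment decrease disqualifies all later deteriorations; on the other, a discounted deterioration is missed if stable and dated late if it continues. Both lengthen the relapse-free interval in 8.3.1.

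The effect on one-year local control holds only if that rate is scored from 8.2. Its size cannot be fixed from the document. The rise in acceptance from 27% to 43–60% (8/25) or from 15% to 27–43% (9/25) assumes the cut-offs, 5–10% of failures unscored, and unscored failures counted as controlled; it is bounded by one-year survival if deaths count as failures. Larger losses, such as 20% or 30% of failures, would put apparent control at 40% or 47.5%, above the survival range in 1.1, and should not be used as headline figures.

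Severity: should-fix. This is a 25-patient non-randomized study, but the endpoint rule should give one answer per patient.

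**What to change.** - In 8.2.3, use a single window: no steroid decrease *since the assessment used for comparison*.
- When a decrease blocks a call, keep the pre-decrease assessment as the reference. If definite deterioration against it is still present at the next assessment without a further decrease, record progression, dated to the first deterioration.
- Do not count death as progression automatically, since that would turn toxic or intercurrent deaths into tumour progression. Report death under overall survival (8.3.2) and state how it counts for one-year control.
- Record the steroid dose at each follow-up assessment. 6.2.4 already asks for dexamethasone doses, but as part of toxicity documentation; the parameter lists in 8.1.1 and Appendix VI have no steroid item.

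The cost is a few sentences in 8.2.3 and one data item per visit. The small downside is that some calls are settled one visit later, with the date carried back.

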2.0 OBJECTIVES

- 2.1 To lay the basis for a randomized phase III of misonidazole and neutron radiation versus misonidazole and photon radiation.
- 2.2 To determine the tolerance of the unusual radiation fraction scheme proposed in this protocol in terms of acute and late normal tissue reaction and damage.
- 2.3 To establish that the tumor clearance rate, disease-free interval and local tumor control rate are within the expected ranges for malignant gliomas.

0015926

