10.0 STATISTICAL CONSIDERATIONS

- 10.1 This study is a non-randomized Phase I/II evaluation of the combination of misonidazole and neutron radiation for malignant glioma.
- 10.2 In general, 25 patients will be entered into the protocol although termination or dose modification may occur earlier if undue toxicity occurs or if response is completely beyond the limits expected. The protocol will be open to all members who have approved laboratories for the measurement of misonidazole levels and who have access to neutron treatment facilities.

With this sample size we have a 93% chance of seeing any complication that occurs one time out of ten. Furthermore, we have over a 90% chance of accepting the treatment for further testing if the actual local control rate of the new treatment is 45% at one year and less than 25% chance of further testing if the actual control rate at one year is 25%.

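### The relapse-free interval in 8.3.1 has no event for death, and the one-year local control rate behind the decision in 10.2 is undefined, so deaths without documented deterioration may escape being counted as failures

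*Protocol*

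**What the plan says.** Protocol 8.3 defines two endpoints. For the first, 8.3.1 says: "Relapse free interval will be measured from the first day of treatment until deterioration is documented as defined in 8.2". The second, overall survival (8.3.2), is the only one in which death is an event.

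Under 8.2.3, progression is a definite (-2) worsening on the neurological examination or on CT. A suspected (-1) change does not count, and a simultaneous steroid reduction cancels the call. Under 8.2.5, assessments fall midway through treatment, at the end of radiotherapy, and then at three-month intervals. In the table in 8.1.1, CT at follow-up carries the footnote "b) If indicated", while the neurological assessment is required at each follow-up.

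Section 10.2 sets the size: "In general, 25 patients will be entered into the protocol". On the decision it says that "we have over a 90% chance of accepting the treatment for further testing" when the true one-year local control rate is 45%, and it puts that chance below 25% when the true rate is 25%. It neither defines the control rate nor gives a cutoff. Objective 2.3 asks for something else, namely that the clearance rate, the disease-free interval and the "local tumor control rate are within the expected ranges for malignant gliomas".

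**The concern.** An interval that only documented deterioration can end has no place for a patient who dies first. Section 1.1 puts survival at 55-67% at 6 months and 27-39% at 12 months, so 33-45% are dead by 6 months and 61-73% by one year. It also says that local growth, not metastasis, is what kills. A death in this population is therefore usually a local failure, whether or not a -2 change was recorded beforehand.

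The schedule leaves room for unrecorded failures. With about 1.5 months of treatment, the three-monthly visits fall near months 4.5, 7.5 and 10.5. A patient who declines and dies between two visits may have no qualifying examination. Optional CT and the steroid rule add to this.

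At stake is the reported relapse-free interval and, if the one-year control rate in 10.2 is taken from it, the decision whether to test the combination further.

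**Working it through.** **The plan's own figures.** The chance of seeing a 1-in-10 complication with 25 patients is 1 - 0.9^25 = 0.928, which agrees with the stated 93%. For the decision rule, P(accept) = P(X ≥ r) with X binomial (25, p). The protocol gives no r, so the two nearest candidates were tried:

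| Cutoff r (assumed) | Method | Accept at 45% | Accept at 25% |
|---|---|---|---|
| 8 | exact | 93.6% | 27.3% |
| 9 | exact | 86.6% | 14.9% |
| 8 | normal approximation, no continuity correction | 90.4% | 21.0% |

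The stated bounds (over 90%, under 25%) are met at n = 25 by the uncorrected normal approximation with r = 8. I use r = 8 with exact probabilities below and show r = 9 for comparison. Neither cutoff is in the protocol.

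**Adding deaths without documented deterioration.** Let the true proportion alive and controlled at one year be 0.25, and let d be the proportion of all patients who die within the year with no documented -2 change. The protocol gives no value for d. I assume 1 or 2 of 25, so d = 0.04 or 0.08. Three handlings do not score these deaths as failures:

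- excluded: apparent rate = 0.25 / (1 - d)
- censored at death, with proportional hazards: apparent rate = 0.25^(1 - d/0.75)
- counted as controlled: apparent rate = 0.25 + d

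| Handling | d = 0.04: apparent rate | accept, r = 8 (r = 9) | d = 0.08: apparent rate | accept, r = 8 (r = 9) |
|---|---|---|---|---|
| Scored as failure | 25.0% | 27% (15%) | 25.0% | 27% (15%) |
| Excluded | 26.0% | 32% (18%) | 27.2% | 36% (22%) |
| Censored | 26.9% | 35% (21%) | 29.0% | 44% (28%) |
| Counted as controlled | 29.0% | 44% (28%) | 33.0% | 62% (45%) |

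Keeping n = 25 in the excluded and censored rows is an approximation, since those patients do not contribute full information. The direction is the same in all three rows and at both cutoffs; the size depends on the handling, on d and on r.

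**Objective 2.3 beside 10.2.** Objective 2.3 is met by rates inside an expected range for which it gives no figures. Section 10.2 is built to accept at 45% and usually not at 25%. These are different criteria, and the protocol does not connect them.

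**The case against.** The strongest reply is that nothing ties 8.3.1 to 10.2. Objective 2.3 lists the disease-free interval and local control as separate measures, and Appendix VI records local disease status at every dose and follow-up visit, which could be the source of the control rate. The protocol states no censoring rule. Section 10.2 reads as a proportion at one year, and a patient dead by then may simply be scored as a failure; a statistical analysis plan could say so. This stands: the effect on the decision is conditional. It does not rescue 8.3.1, which is a fixed definition in the protocol and omits death.

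It is also fair that undocumented deaths may be few. Progression needs no CT, the neurological assessment is required at each follow-up, patients on drug are assessed before each treatment, a follow-up form is due at death (9.2), and autopsy is sought. A reader might infer from the 61-73% one-year mortality that many deaths would go uncounted. Only deaths with no earlier -2 change matter, and the protocol gives no figure for those. If one fifth of the failure hazard is assumed to be such deaths and they are censored, the apparent rate is 0.25^0.8 = 0.33 and acceptance at 8 of 25 is 62%. The arithmetic is correct, but nothing in the protocol supports that share.

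A reader might also infer that a patient who dies of neutron brain damage with the tumor destroyed would count in favor of the treatment. Under 8.2.3 a definite neurological decline counts whatever its cause, so such a patient, if examined, is a progression. Section 1.1 reports autopsy findings from the pilot series but does not link them to cause of death.

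Finally, 7 of 25 (28%) might be said to satisfy 2.3 and fail 10.2. That needs an assumed cutoff and needs the 27-39% survival range to stand in for an unstated control range. Only the mismatch in wording is established.

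**Conclusion.** The point holds for the definition and conditionally for the decision. As written, 8.3.1 does not count a death without a documented -2 change as a failure, which biases the relapse-free interval upward in a disease where most patients die within a year and local growth is the stated cause. The one-year local control rate in 10.2 is undefined. If it is read from 8.3.1 and such deaths are not scored as failures, acceptance of a treatment with a true rate of 25% rises from 27% to 32-44% (excluded or censored) or 44-62% (counted as controlled). Those figures assume a cutoff of 8 of 25 and 1-2 such deaths, neither of which is in the protocol. If the deaths are scored as failures, there is no inflation. Separately, 2.3 and 10.2 state different criteria and should be reconciled.

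**What to change.** - **8.3.1:** end the interval at the first of progression under 8.2.3 or death from any cause.
- **10.2:** define one-year control as alive without progression 12 months from first treatment, with all entered patients in the denominator. Confirm that the 25% and 45% benchmarks apply to that definition. A rate that counts death as failure cannot exceed survival, which 1.1 puts at 27-39% at 12 months, so the benchmarks cannot be carried over unexamined.
- **2.3:** refer to the criterion in 10.2.
- **Secondary reporting:** give cause-specific or autopsy-based local control alongside.

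No new data are needed: death dates are already required for 8.3.2 and a form is due at death. The cost is a lower reported control rate, the counting of deaths unrelated to tumor as failures (which the secondary report helps to separate), and the work of justifying the benchmarks again.
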